10.2.3 Worst Itch Numerical Rating Scale (WI-NRS)

WI-NRS Assessments will be performed as follows: Screening, Baseline, Week 1, Week 2, and Week 4.

The WI-NRS has been developed as a simple, single item to assess the patient-reported severity of this symptom at its highest intensity during the previous 24-hour period. ([Naegeli 2015](#)). The WI-NRS will be determined by asking the subject's assessment of worst itch over the past 24 hours. The scale is from '0 to 10' ("no itch" to "worst imaginable itch"). Subjects will complete the WI-NRS pruritus assessment.

10.3 Other Evaluations

10.3.1 Body Surface Area (BSA)

BSA Assessments will be performed as follows: Screening, Baseline, Week 1, Week 2, and Week 4.

The BSA affected by atopic dermatitis will be determined by the subject's hand method, where the subject's hand (including fingers) surface area is assumed to equal 1% of body surface area (BSA).

Note: All atopic dermatitis lesions on a subject will be treated including the face, trunk, genitals/skin folds, or limbs (excluding the scalp). The palms and soles will be treated but will not be counted towards any measurements of efficacy (EASI, IGA, BSA).

Body Diagram

The body diagram (see [Appendix 1](#)) will be completed as follows: Baseline.

A copy of the body diagram will be provided to the subject for study drug application at home.

10.3.2 Pharmacokinetics Assessment

PK draws will be performed as follows for all subjects at all sites:

- For the serial PK subset enrolled under the previous amendment: On the first day of dosing, PK draws will be done pre-dose and at 1, 2, 4, 6 and 24 hours post-dose administration. On Day 15, PK draws will be taken at pre-dose, 1, 2, 4, 6, and 24 hours post-dose administration
- For all subsequent subjects enrolled under this amendment: PK draws will be collected at Days 1 and 29. The single draw will be pre-dose drug application in the clinic.

Ensure study medication is not applied in the area where PK will be drawn.

10.4 Final Study Visit

The approximate final study visit will occur at Week 4 (Day 29). The procedures performed during these visits are as described in Schedule of Events ([Section 5](#)). A 3-day scheduling leeway period is allowed for this visit.

10.5 Early Termination Visit

If a subject is withdrawn or wishes to exit the study, a termination visit will be scheduled. This visit should include the procedures and assessments that would be performed at the Week 4 visit (Day 29).

10.6 Unscheduled Visit

Unscheduled visits may be necessary to repeat testing following abnormal laboratory results, for follow-up of AEs, or for any other reason, as warranted in the judgement of the Investigator.

The following information will be collected for all subjects:

- Concomitant medications/procedures
- AEs

The following information also will be collected:

- vIGA-AD and EASI
- BSA affected with AD
- Local tolerability assessment

The rules for how to tally vIGA-AD, BSA or other proportions of categorical responses will be described in the Statistical Analysis Plan.

10.7 Adverse Events

10.7.1 Adverse Event Definition

An AE means any untoward medical occurrence associated with the use of a drug in humans, whether or not considered drug related. An AE can therefore be any unfavorable and unintended sign (including an abnormal laboratory finding), symptom, or disease temporally associated with the use of a medicinal (investigational) product, whether or not related to the medicinal (investigational) product.

AEs will be collected following informed consent of the subject until one month after treatment.

A treatment emergent adverse event (TEAE) is defined as an AE that started post application of study medication at the Baseline visit or was present at treatment initiation but worsened during treatment, through study completion.

Application site reactions will be considered adverse events if they require intervention, suspension or discontinuation of study drug.

10.7.2 Serious Adverse Event

The definitions and reporting requirements of the Food and Drug Administration (FDA)/ICH Guidelines for Clinical Safety Data Management, Definitions and Standards for Expedited Reporting, Topic E2A will be adhered to. If any AEs are serious, as defined by ICH Guidelines for Clinical Safety, required procedures will be followed. All SAEs will be reported to the Sponsor via fax or e-mail within 24 hours of becoming aware of the event, whether or not the serious events are deemed drug-related. All serious event reporting will adhere to ICH E6: Guideline for Good Clinical Practice and ICH E2A: Clinical Safety Data Management: Definitions and Standards for Expedited Reporting. The IRB will be notified of the Alert Reports as per FDA, ICH and the IRB's policies and procedures.

An SAE is any AE that in the view of either the PI or Sponsor, results in any of the following outcomes: Death, a life-threatening AE, inpatient hospitalization or prolongation of existing hospitalization, a persistent or significant incapacity or substantial disruption of the ability to conduct normal life functions, or a congenital anomaly/birth defect. Important medical events that may not result in death, be life-threatening, or require hospitalization may be considered serious when, based upon appropriate medical judgment, they may jeopardize the subject and may require medical or surgical intervention to prevent one of the outcomes listed in the above definition. Examples of such medical events include allergic bronchospasm requiring intensive treatment in an emergency room or at home, blood dyscrasias or convulsions that do not result in inpatient hospitalization, or the development of drug dependency or drug abuse.

Life-threatening is defined as an AE that in the view of the PI or Sponsor, places the subject at immediate risk of death. It does not include an AE that, had it occurred in a more severe form, might have caused death.

Hospitalization does not include the following:

- Rehabilitation facilities, hospice facilities or respite care (e.g. caregiver relief)
- Nursing homes or skilled nursing facilities
- Emergency room visits
- Same day surgeries (as outpatient/same day/ambulatory procedures)
- <24 hour admissions for observation or evaluation

Hospitalization or prolongation of hospitalization in the absence of a precipitating, clinical AE is not in itself an SAE. Examples include:

- Admission for treatment of a preexisting condition that did not worsen
- Hospitalizations for cosmetic elective surgery, social, and/or convenience admissions
- Pre-planned treatments or surgical procedures should be noted in the baseline documentation for the individual subject.
- Diagnostic and therapeutic procedures, such as surgery, should not be reported as AEs; however, the medical condition for which the procedure was performed should be reported if it occurs during the reporting period and meets the definition of an AE. For example, an acute appendicitis that begins during the AE reporting period should be reported as an AE, and the resulting appendectomy should be recorded as treatment of the AE.

Unexpected is defined as an AE that is not listed in the IB or is not listed at the specificity or severity that has been observed; or is not consistent with the risk information described in the general investigational plan or elsewhere in the current IND.

If a SAE occurs to a subject on this study, contact the Sponsor personnel listed in [Section 2](#) within one business day of knowledge of event.

10.7.3 Suspected Unexpected Serious Adverse Reaction (SUSAR)

This is defined as a serious adverse reaction, the nature or severity of which is not consistent with the known study treatment information. A serious event or reaction is not defined as a SUSAR when: 'it is serious but expected' or it does not fit the definition of an SAE, whether expected or not.

10.7.4 Safety Review with Subject

At each follow-up visit, subjects will be queried with an open-ended question such as: 'How have you been feeling since your last visit?' Additionally, the study staff will review subject

diaries and, if it appears that a potential AE was recorded, study staff will query the subject and determine if an AE occurred.

AEs (whether serious or non-serious) and clinically significant abnormal laboratory test value(s) will be evaluated by the PI and treated and/or followed up for up to one month after end of treatment until the symptoms or value(s) return to normal, or acceptable levels, as judged by the PI.

Where appropriate, medical test(s) and/or examination(s) will be performed to document resolution of event(s). Outcome may be classified as resolved, improved, unchanged, worse, fatal or unknown (lost to follow-up).

10.7.5 Adverse Event Reporting

The PI will review each event and assess its relationship to drug treatment (unrelated, unlikely, possibly, probably, likely). Each sign or symptom reported will be graded on the NIH NCI CTCAE toxicity grading scale 5-point severity scale (Grade 1, 2, 3, 4 and 5). The date and time of onset, time relationship to drug dosing, duration, and outcome (resolved, improved, unchanged, worse, fatal, or unknown/lost to follow-up) of each event will be noted.

- The relationship of each AE to the study drug will be assessed using the following definitions:

Unrelated	
• The AE must clearly be caused by the subject's clinical state, or the study procedure/conditions.• Definitely not related to drug.• Temporal sequence of an AE onset relative to administration of drug not reasonable.• Another obvious cause of an AE.
Unlikely	
• Time sequence is unreasonable.• There is another more likely cause for an AE.
Possibly	
• Corresponds to what is known about the drug.• Time sequence is reasonable.• Could have been due to another equally, likely cause.
Probably	
• Is a known effect of the drug.• Time sequence from taking drug is reasonable.• Ceases on stopping the drug.• Cannot be reasonably explained by the known characteristics of the subject's clinical state.
Likely	
• Is a known effect of the drug (e.g., listed in Physicians' Desk Reference, Compendium of Pharmaceuticals and Specialties, IB).• Time sequence from taking drug is reasonable.• Event stops upon stopping drug, event returns upon restarting drug.

- The following CTCAE toxicity grading scale 5-point severity scale definitions for rating maximum severity will be used:

Grade 1	Mild; asymptomatic or mild symptoms; clinical or diagnostic observations only; intervention not indicated.
Grade 2	Moderate; minimal, local or noninvasive intervention indicated; limiting age-appropriate instrumental activities of daily living.*
Grade 3	Severe or medically significant but not immediately life-threatening; Hospitalization or prolongation of hospitalization indicated; disabling; limiting self-care activities of daily living.** Note: An experience may be severe but may not be serious, e.g., severe headache).
Grade 4	Life-threatening consequences; urgent intervention indicated.
Grade 5	Death related to AE.

Note: A semi-colon indicates 'or' within the description of the grade.

* Instrumental activities of daily living refer to preparing meals, shopping for groceries or clothes, using the telephone, managing money, etc.

** Self-care activities of daily living refer to bathing, dressing and undressing, feeding self, using the toilet, taking medications, and not bedridden.

AEs will be coded using the most current MedDRA® version available at the start of the study.

10.8 Reporting Pregnancy

During the study, all subjects should be instructed to contact the investigator immediately if they suspect they might be pregnant (e.g., missed or late menstrual period). If pregnancy is confirmed, the subject will be withdrawn from the study and followed until the pregnancy comes to term.

The investigator is responsible for reporting all available pregnancy information on the pregnancy report within 24 hours of becoming aware of the event, although pregnancy itself is not considered an AE. Study treatment must be discontinued immediately in the event of a pregnancy. The subject should be referred to an obstetrician/gynecologist experienced in reproductive toxicity for further evaluation and counseling. Monitoring of the subject should continue until the conclusion of the pregnancy. Follow-up information detailing the outcome of the pregnancy and the health of the newborn should be reported as it becomes available.

Partner pregnancies of a male subject do not need to be reported.

Any pregnancy complication or premature terminations including miscarriage, spontaneous abortion or elective termination of a pregnancy for medical reasons will be reported as an SAE, as described in [Section 10.7.2](#). Should the pregnancy result in a congenital abnormality or birth defect, a separate SAE report must be submitted. Furthermore, all neonatal deaths that occur within 30 days of the birth should be reported as SAEs, without regard to causality. In addition,

any infant death that occurs after the 30-day reporting period that the investigator suspects are related to the in-utero exposure to the study treatment should also be reported.

10.9 Treatment Stopping Rules

If a subject has non-cutaneous adverse events of concern, clinically significant laboratory values or any condition that the investigator determines could possibly be related to the study drug, the Investigator should immediately contact the Medical Monitor to discuss if the subject should be discontinued from the study.

Treatment for any individual subject will be discontinued if the subject:

- Experiences a serious adverse event (SAE) or a clinically significant non-serious AE which in the opinion of the Principal Investigator or Medical Monitor warrants discontinuation from the study for that subject's well-being.
- A severe (Grade 3) laboratory abnormality (confirmed by repeat sample and considered related to study drug).

Dosing of study drug for an individual subject may be suspended for safety concerns other than those described above, at the discretion of the investigator if he/she feels the subject's safety may be threatened.

A subject with a PHQ-8 score of '15' or above should be referred promptly to a mental health care professional and consideration be given to discontinuation from study drug.

A subject that is experiencing suicidal ideation and behavior should be referred immediately to a qualified mental health care provider and consideration given to discontinuation from study drug.

As noted above, study treatment must be discontinued immediately in the event of a female subject's pregnancy.

Treatment should be interrupted:

- If a subject develops an application site reaction with the clinical appearance of an 'irritation reaction', and with a severity of a Dermal Response Score of 5 (erythema, edema and papules) or greater on the scale of Berger and Bowman, treatment should be interrupted for up to one week and may then be resumed if the reaction has, in the opinion of the Investigator, adequately resolved.

Treatment should be discontinued:

- If the reaction reoccurs, treatment should be discontinued permanently, and the subject followed until the reaction resolves.

For cases of suspected allergic contact dermatitis, the medical monitor and sponsor should be notified and there should be discussion about performing patch testing to further evaluate. Patch testing is encouraged in such cases.

11 DATA ANALYSIS

Data will be handled and processed according to the Contract Research Organization's Standard Operating Procedures, which are written based on the principles of GCP.

11.1 Statistical Methods

The methodology presented below is a summary of the more detailed analysis plan that will be presented in the Statistical Analysis Plan (SAP). The SAP will be finalized before the database is locked and unblinded. Any changes to the methods described in the final SAP will be described and justified in the clinical study report.

All statistical processing will be performed using SAS[®] (Version 9.4 or later) unless otherwise stated. No interim efficacy analyses are planned.

Descriptive statistics will be used to provide an overview of the safety, efficacy, and pharmacokinetic results. For categorical parameters, the number and percentage of subjects in each category will be presented. The denominator for percentage will be based on the number of subjects appropriate for the purpose of analysis. For continuous parameters, descriptive statistics will include n (number of subjects), mean, standard deviation (SD), median, minimum, and maximum.

11.1.1 Pharmacokinetics Assessment

Plasma levels of circulating roflumilast and its major N-oxide metabolite will be measured at the following time points:

- Prior to study drug application on Days 1 and 29
- Pre-dose, 1, 2, 4, 6 hrs post dose on Days 1 and 15, and 24 hrs post dose on Days 2 and 16 (serial PK subgroup enrolled under previous amendment only)

11.1.2 Pharmacokinetic Parameters

All subjects who are enrolled and receive at least one application of study drug, and have sufficient pharmacokinetic assessments will be included in the pharmacokinetic population.

When possible, the exposure of roflumilast and its major N-oxide metabolite will be calculated based on plasma concentrations versus time profile data and compared between the treatment groups.

A detailed description of the PK analysis will be presented in the SAP.

11.1.3 Safety Analysis

The following analyses will be performed; however, no formal inferential statistics will be done on safety assessments.

Descriptive statistics will be presented by visit for quantitative safety data and frequency counts will be compiled for classification of qualitative safety data. Summaries of local tolerability will be presented by visit.

Adverse Events:

All treatment-emergent AEs occurring during the study will be recorded and classified on the basis of MedDRA terminology for the safety population. Treatment-emergent AEs are those AEs with an onset on or after application of study medication at the Baseline visit or were present at treatment initiation but worsened during treatment, through study completion. All treatment-emergent AEs will be summarized by treatment group, the number of subjects reporting treatment-emergent AEs, system organ class, preferred term, severity, relationship, and seriousness.

Comparisons between treatment groups will be made by tabulating the frequency of subjects with one or more treatment-emergent AEs (classified into MedDRA terms) during the study.

Serious adverse events (SAEs) will be listed by subject. SAEs will be summarized by severity, and relationship to study treatment. Each subject will be counted only once within a system organ class or a preferred term using the event with the greatest relationship and greatest severity.

All information pertaining to AEs noted during the study will be listed by subject, detailing the verbatim description given by the Investigator, preferred term, system organ class, start date, stop date, severity, action taken regarding study drug, corrective treatment, outcome, and drug relatedness. The event onset will also be shown relative (in number of days) to date of first application. In addition, a list of subjects who prematurely discontinue from the study due to adverse events will also be provided.

A subject-by-subject treatment-emergent AE (TEAE) data listing, including verbatim term, preferred term, treatment, severity, and relationship to study drug, will be provided.

Medical history will be listed by subject. Physical examinations performed at Screening, Baseline and Week 4, and 12-lead ECGs will be performed at Screening and Week 4. Both physical examination and ECG results will be listed by subject.

Vital signs will be tabulated by visit and treatment group.

ECGs will be tabulated by visit and treatment group.

Laboratory testing will be obtained throughout the study and the results summarized by parameter, visit and treatment group.

11.1.4 Determination of Sample Size

The sample size will be approximately 90 to 105 subjects. A subset of subjects enrolled under the previous amendment will receive serial PK sampling.

A sample size of 27 per arm will provide at least 80% power to detect a difference in the mean change from baseline in EASI Total Score of 35% at week 4 (for each ARQ-151-treated group versus vehicle-treated group), assuming a pooled standard deviation of 40%, with a two-sided $\alpha = 0.05$. This is based on a 2-sample t-test. This includes P value adjustment for multiplicity using Bonferroni correction. With a 10-25% dropout rate, the sample size for the study would be increased to 30-35 subjects per arm (90-105 subjects total). Change from baseline in EASI Total Score at week 4 is expected to provide more statistical power than percent change from baseline in Total EASI Score at this timepoint (which is a secondary endpoint) and has been chosen as the primary endpoint.

This sample size is considered adequate for PK and safety evaluation.

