9 INVESTIGATIONAL PLAN

9.1 Overall Study Design and Plan

This is a phase 2, parallel group, double blind, vehicle-controlled study of ARQ-151 cream 0.15% and ARQ-151 cream 0.05% QD applied for 4 weeks to adolescent and adult subjects with 1.5% to 35% BSA of mild to moderate atopic dermatitis. A subset of subjects that consented under the previous amendment will have serial PK testing, while only trough PK sampling will be performed for all new subjects enrolled under this amendment.

A total of up to approximately 90 to 105 subjects will be enrolled at approximately 30 study sites in the United States and Canada. Subjects will be adolescent (12-17 y/o) or adult (≥ 18 y/o) males or females with atopic dermatitis. Subjects must have an Investigator's Global Assessment of disease severity (vIGA-AD) of Mild ('2') or Moderate ('3') at Baseline. Subjects must have at least 1.5% and no more than 35% BSA of atopic dermatitis (excluding scalp, palms, and soles). All atopic dermatitis lesions on a subject will be treated including the face, trunk, genitals/skin folds, or limbs (excluding the scalp). The palms and soles will be treated but will not be counted towards any measurements of efficacy (EASI, vIGA-AD, BSA).

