### 6.5 Statistical Tests

Unless otherwise specified, all statistical tests will be two-sided and will be performed with a significance level of 0.05. Confidence intervals (CIs) will be two-sided with 95% coverage.

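### Minor: 27 evaluable subjects per arm at 25% dropout needs 36 randomised per arm, not the stated 35; the power effect is negligible unless enrolment stops near 90 with dropout clearly above 10%

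*Protocol*

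**What the plan says.** Protocol 11.1.4 sets the size in two steps. First: "A sample size of 27 per arm will provide at least 80% power to detect a difference in the mean change from baseline". This applies to each active arm against vehicle. The inputs are a "difference in the mean change from baseline in EASI Total Score of 35% at week 4", "assuming a pooled standard deviation of 40"%, a two-sample t-test, two-sided alpha of 0.05, and a Bonferroni correction. Second, the inflation for dropout: "With a 10-25% dropout rate, the sample size for the study would be increased to 30-35 subjects per arm (90-105 subjects total"). The Protocol Synopsis (Power and Sample Size) and SAP 5.1 repeat both steps.

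Other passages bear on the point:

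- Protocol 9.1 gives enrolment as a range: "A total of up to approximately 90 to 105 subjects will be enrolled at approximately 30 study sites in the United States and Canada". No section says where in that range enrolment closes.
- Protocol 9.8 and SAP 3.4.2 allow subjects who leave to be replaced but do not require it.
- SAP 6.6 uses Dunnett's method, not Bonferroni, for the two primary comparisons.
- SAP 6.2 and 12.1 analyse the primary endpoint by MMRM in the ITT population, without imputation.

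**The concern.** The stated power belongs to 27 evaluable subjects per arm, so the inflated size has to leave 27 after the stated dropout. It does at 10% and does not at 25%, so the sentence is arithmetically wrong at its upper end in all three places.

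This calculation is the only quantitative justification of the trial's size. If the trial closed near 90 with dropout well above 10%, a null result for one dose would be read against 80% power when the plan's own method gives somewhat less. If dropout and enrolment rise together, as the sentence suggests, almost nothing is at stake.

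**Working it through.** **Inputs.** Difference 35, SD 40, two-sample t-test, overall two-sided alpha 0.05, Bonferroni over two comparisons, 27 per arm, dropout 10-25%, 30-35 per arm (Protocol 11.1.4). Dunnett comes from SAP 6.6. The percentage inputs are taken at face value.

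**Step 1: reproduce the 27.** Standardised difference = 35/40 = 0.875. Alpha per comparison = 0.05/2 = 0.025, two-sided. Power comes from the noncentral t distribution with 2n - 2 degrees of freedom and noncentrality 0.875 × √(n/2).

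- n = 26: 79.8%
- n = 27: 81.5%

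So 27 is the smallest whole number that reaches 80%, and the plan's figure is reproduced. Without Bonferroni the t-test needs 22, which confirms that 27 includes the correction.

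**Step 2: inflate for dropout.** Randomised n = 27/(1 - d), rounded up.

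| Dropout d | 27/(1 - d) | Needed per arm |
|---|---|---|
| 10% | 30.0 | 30 |
| 15% | 31.8 | 32 |
| 20% | 33.75 | 34 |
| 25% | 36.0 | 36 (108 total) |

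The stated 30 is exact. The stated 35 is one short per arm, three in total.

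**Step 3: the dropout each size can absorb while keeping 27.** At 35 per arm: 1 - 27/35 = 22.9%. At 30 per arm: 1 - 27/30 = 10%.

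**Step 4: power at the sizes left.** The Bonferroni column is as in step 1. The Dunnett column uses two comparisons with a shared control (correlation 0.5), a pooled error with 3n - 3 degrees of freedom, and a critical value of about 2.25-2.26.

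| Per arm | Dropout | Evaluable per arm | Bonferroni | Dunnett |
|---|---|---|---|---|
| 30 | 10% | 27 | 81.5% | 83.0% |
| 35 | 25% | 26.25 (26 in whole subjects) | 80.2% (79.8% at 26) | about 81-82% (81.4% at 26) |
| 30 | 20% | 24 | 76.0% | about 78% |
| 30 | 25% | 22.5 (22 to 23) | 71.7% to 73.9% | 73.8% to 75.9% |

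The first two rows are the pairs that the sentence suggests. The last two combine the smallest size with higher dropout; the text neither makes nor rules out that combination.

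**Step 5: the same check under Dunnett alone.** Power is 79.7% at 25 evaluable and 81.4% at 26, so 26 is enough. Then 26/0.75 = 34.7, which rounds up to 35: under the planned test the stated upper end does cover 25% dropout. At 30 per arm the limit becomes 1 - 26/30 = 13.3%.

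**The case against.** The best defence is that two ranges in one sentence read naturally as paired, 30 with 10% and 35 with 25%, and that the numbers are described as approximate. On that reading the lower end is exact, the upper end is one subject per arm out, and SAP 6.6's Dunnett test removes even that gap. This stands, and it is why the point is minor. It does not make the sentence correct as written, because the sentence rests on 27 evaluable under Bonferroni, and 35 per arm does not leave 27 at 25% dropout.

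A second defence is that leavers are not wholly lost. They may be replaced. They have an early termination visit (Protocol 10.5), which counts as Week 4 if it falls on Days 22-32 (SAP 5.4). The MMRM also uses their Week 1 and Week 2 data and adjusts for baseline EASI and vIGA-AD stratum. All of this is fair and pushes power up. The documents give neither visit correlations nor the variance explained by the covariates, so the gain cannot be put in numbers, and the plan's own calculation takes no credit for it.

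A reader might go further and infer that the trial has only about 72% power, or that the stated size fails over most of its own range. The documents do not support that. The 72% figure joins the smallest enrolment to the worst dropout under the more conservative correction, and no section says that 30 per arm covers 25% dropout. A reader might also want a rule keeping randomisation open beyond 90 unless dropout is at or below 10%. That is a design preference, not a correction. Final dropout is not fully known when randomisation closes, and under Dunnett 10% is a tighter trigger than needed.

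**Conclusion.** The stated inflation is wrong as written, but minor. At 25% dropout, 27 evaluable per arm needs 36 randomised per arm (108 in total), not 35 (105).

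Read as paired, the power effect is negligible: about 80% with Bonferroni and about 81% with Dunnett at 35 per arm and 25% dropout. Apart from that marginal case, the 80% figure is missed by the plan's own method only if enrolment stops near 90 and dropout is clearly above 10%. At 30 per arm the figures are then about 76% or 78% at 20% dropout, and about 72-74% or 74-76% at 25%.

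These results assume that the 35 and 40 inputs hold for the analysed endpoint, that dropout is equal across arms, and that a subject who drops out contributes nothing. The last assumption is pessimistic for the planned MMRM.

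**What to change.** Restate the dropout sentence in the Protocol Synopsis, Protocol 11.1.4 and SAP 5.1. Suggested text:

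*27 evaluable subjects per arm require 30 randomised per arm at 10% dropout and 36 at 25%. With 35 per arm, power at 25% dropout is about 80%. With 30 per arm, at least 80% power is kept up to about 10% dropout (about 13% under Dunnett), and falls to about 72-76% at 25% dropout.*

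The cost is one sentence in three places. Planned enrolment, conduct and analysis do not change, and no rule for closing enrolment is needed. The stated power becomes slightly less favourable for a trial that closes at the low end of its range.
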